8.3.4 BIOMARKER ANALYSIS

8.3.4.1 TAPE STRIPPING

Tape strip samples will be collected from non-lesional and lesional skin according to the SoA ([Section 1.3](#)) to measure cutaneous biomarkers including but not limited to IL-36R, Th-17 cytokines such as IL-17A, and markers of neutrophils and dendritic cell infiltration.

The actual date and time of the sample collection will be recorded in the subject's eCRF. The details of tape strip collection, sample tube labeling, sample preparation, storage, and shipping procedures will be described in a separate Laboratory Manual.

The measurement of tape strip biomarkers may be performed by an additional third party (eg, a university Investigator) designated by AnaptysBio.

9 STATISTICAL CONSIDERATIONS

9.1 STATISTICAL HYPOTHESES

The primary analysis for this study is to compare the mean facial inflammatory lesion count for imsidolimab with placebo during the treatment period, at a two-sided alpha = 0.10 level. Any testing being performed for secondary or exploratory endpoints will be considered exploratory in nature based on a 2-sided alpha = 0.10

$H_0: \mu_{\text{imsidolimab}} - \mu_{\text{placebo}} = 0$ vs. $H_A: \mu_{\text{imsidolimab}} - \mu_{\text{placebo}} \neq 0$

9.2 SAMPLE SIZE DETERMINATION

Approximately 120 subjects will be stratified based on facial IGA score at baseline (3 [moderate] versus 4 [severe]) and randomized in a 1:1:1 ratio to receive one of the following study treatments:

- Imsidolimab 400 mg on Day 1, 200 mg on Days 29 and 57
- Imsidolimab 200 mg on Day 1, 100 mg on Days 29 and 57
- Placebo on Days 1, 29, and 57

For this Phase 2 study, the sample size was chosen empirically. Assuming a total of 10% of subjects will discontinue prior to Week 12, there will be approximately 108 evaluable subjects (36 subjects in each arm) at the end of Week 12.

The study has 80% power to detect a between-group treatment difference of 6.1 lesions in the primary endpoint of mean change from baseline in the AN count at Week 12, using a 2-sided, equal-variance two-sample t-test at the $\alpha = 0.10$ level, with the assumption of a common standard deviation (SD) of 10.4 lesions. The assumption was based on Arazlo (tazarotene) acne Phase 3 Study Trial-301 results (Ararzlo 2019). Table 6 shows more information on power from a set of scenarios of variability and between-group mean differences.

Table 6: Power Exploration for Different Scenarios of Variability and Between-group Mean Differences

Common Standard Deviation (SD)	Between-group mean difference	Power (%)	
		1-sided test	2-sided test
8	3	62	48
	4	80	68
	5	92	84
	6	97	94
10	3	50	36

Efficacy and Safety of Imsidolimab in Subjects with Acne Vulgaris
Protocol ANB019-209

Version 1.0
11 February 2021

Common Standard Deviation (SD)	Between-group mean difference	Power (%)	
		1-sided test	2-sided test
	4	66	52
	5	80	68
	6	90	82
12	3	41	28
	4	55	41
	5	69	55
	6	80	68

Note: An equal variance two-sample t-test at alpha=0.10 is used for the power calculations.

9.3 POPULATIONS FOR ANALYSES

The analysis sets are defined in [Table 7](#).

Table 7: Analysis Sets

Analysis Set	Description
ITT Analysis Set	The ITT analysis set will include all randomized subjects. In this analysis set, treatment will be assigned based upon the treatment arm to which subjects were randomized regardless of which treatment they receive. ITT analysis set will be used for primary, secondary and exploratory efficacy analyses.
Safety Analysis Set	The safety analysis set will include all randomized subjects who receive 1 dose of imsidolimab or placebo. The safety analysis set will be used for all safety analyses. Subjects will be analyzed as treated.
Per Protocol Analysis Set	The per protocol analysis set will include all subjects in the ITT analysis set who do not have major protocol violations that would affect the evaluation of the primary efficacy endpoint.
PK Analysis Set	The PK analysis set will include all imsidolimab-treated subjects in the safety analysis set who have at least 1 quantifiable postdose PK sample available and who do not have events or protocol deviations or events with the potential to affect PK concentrations. The PK analysis set will be used for all PK analyses.

Abbreviations: ITT, intent-to-treat; PK, pharmacokinetic

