7.1.1 TEMPORARY INTERRUPTION

Study treatment can be interrupted temporarily for any individual subject in case of an AE as per the Investigator's discretion. The Medical Monitor should be informed. Re-starting of study treatment can be done after discussion with the Medical Monitor.

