8.2.1.9 TREATMENT OF OVERDOSE

For this study, any dose of imsidolimab or placebo administered in a volume exceeding the planned dosing detailed in [Table 3](#) (Dose Strength[s]/Dosage Level[s]) will be considered an overdose.

In the improbable event of a suspected overdose, the following procedures should be executed:

- Administration is to be discontinued.
- The subject is to be monitored clinically.
- Supportive measures are to be undertaken as clinically indicated.
- Electrocardiography and clinical laboratory evaluations (ie, blood glucose, hepatic enzymes, creatinine, blood urea nitrogen, creatine kinase (CK), and complete blood count) are to be performed and followed until all values return to Baseline levels and AEs subside, if applicable.

No information on overdose, maximum tolerated dose, or dose-limiting toxicities for imsidolimab has been established at this time and since there are no known antidotes for imsidolimab, the treatment of overdose is at Investigator's discretion.

In the event of an overdose, the Investigator should:

1. Contact the Medical Monitor immediately.
2. Closely monitor the subject for any AE/SAE and laboratory abnormalities and follow-up until resolution.
3. Obtain a serum sample for PK analysis soon after the dose for SC administration.
4. Document the quantity of the excess dose as well as the duration of the overdose in the eCRF.

Decisions regarding dose interruptions will be made by the Investigator in consultation with the Medical Monitor based on the clinical evaluation of the subject.

Efficacy and Safety of Imsidolimab in Subjects with Acne Vulgaris
Protocol ANB019-209

Version 1.0
11 February 2021

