8.3.2 PHARMACOKINETICS

Whole blood will be obtained for the determination of imsidolimab concentration in human serum. Samples will be collected according to the SoA ([Section 1.3](#)) and [Table 5](#). Whole blood will be obtained from each subject for PK assessments during the study. Each serum sample will be divided into 2 aliquots (1 each for primary and a back-up). Samples collected for analyses of imsidolimab serum concentration also may be used to correlate exposure to safety or efficacy as well as supportive analysis for dose justification.

The actual date and time (24-hour clock) of the blood sample collection will be recorded in the subject's eCRF. The details of blood sample collection, sample tube labeling, sample preparation, storage, and shipping procedures will be described in a separate laboratory manual.

The measurement of the concentrations of imsidolimab will be performed using a validated assay method under the supervision of AnaptysBio. The analytical methods used to measure concentrations of imsidolimab will be described in a separate bioanalytical report.

Only samples within the stability window of the assay will be analyzed.

While PK samples must be collected from subjects randomized to the placebo arm to maintain the blinding of treatment assignment, PK assay results for these subjects are not needed for the safe conduct or proper interpretation of this study. These samples may not be analyzed unless needed to investigate if a dosing error has occurred. Personnel at the bioanalytical laboratory performing PK assays will be unblinded, the clinical study team members, and study site staff (with the exception of the unblinded Pharmacist) will remain blinded to treatment for the duration of the study. Data may be de-identified for quality review. Additional details on de-identification or unblinding of the PK data, if applicable, will be described in a separate plan.

Drug concentration information that may unblind the study will not be reported to study sites or blinded personnel until the study has been unblinded.

Table 5: Pharmacokinetic and Anti-drug Antibody Collection Schedule

Study Visit	PK Sample Time Point	ADA Sample Time Point
Day 1	Predose	Predose
	2 hr (\pm 10 min) postdose	
Day 15	Anytime	Anytime
Day 29	Predose	Predose
Day 57	Predose	Predose
Day 85	Anytime	Anytime
Day 141	Anytime	Anytime

Abbreviations: ADA, anti-drug antibody; hr, hours; min, minutes; PK, pharmacokinetic

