### 5.4 Pharmacokinetic Analysis Set

The PK Analysis Set will include all imsidolimab-treated subjects in the Safety Analysis Set who have at least 1 quantifiable post-dose PK sample available and who do not have events or protocol deviations with the potential to affect PK concentrations. The PK Analysis Set will be used for all PK analyses.

The PK Analysis Set will be determined after review of the clinical study data (e.g., concomitant medications, study drug dosing information, and adverse events [AEs]). Prior to the final PK analysis, subject data as well as protocol deviations will be reviewed in a blinded manner by Everest, AnaptysBio, and Innovaderm at the blinded data review meeting (BDRM) for inclusion/exclusion into the PK Analysis Set.

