## 7.6 Pharmacokinetic Analyses

The PK analysis will be performed for subjects in the PK Analysis Set.

Mean trough serum concentration-time data for samples collected on Days 29, 57, and 85 will be tabulated as well as graphically presented as scatter plots. Nominal collection times will be used for graphs.

A subject listing of all concentration-time data following SC injections will be presented by subject and scheduled sample collection time. All concentration data of imsidolimab will be summarized by day and nominal time point using the number of observations, arithmetic mean, SD, CV, minimum, median, maximum, geometric mean, and CV of geometric mean. Concentration time data values reported as below the limit of quantification (BLQ) that occur at pre-dose or prior to the first observed non-BLQ positive concentration will be set to zero or will be set to missing for records that occur after the last quantifiable concentration.

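### The PK Analysis Set drops whole subjects for PK-affecting events, so a late dosing deviation can take valid earlier concentrations out of the PK summaries; sample-level flags would be a cheap improvement.

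*Protocol*

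**What the plan says.** Protocol section 9.3 (Table 7) builds the PK Analysis Set from imsidolimab-treated subjects in the safety set with at least 1 quantifiable post-dose sample, and then keeps only those "who do not have events or protocol deviations or events with the potential to affect PK concentrations". It adds: "The PK analysis set will be used for all PK analyses". SAP section 5.4 has the same restriction without the repeated words: "who do not have events or protocol deviations with the potential to affect PK concentrations". It also says how the decision is made. Medications, dosing records and adverse events are reviewed blind, and each subject is then included in the set or left out.

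SAP section 7.6 applies the set: "The PK analysis will be performed for subjects in the PK Analysis Set". That section plans concentration summaries by nominal day, and trough tables and plots for Days 29, 57 and 85. Its only rule for individual samples concerns values below the limit of quantification.

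Dosing deviations are foreseen. Protocol section 7.1.1 states: "Study treatment can be interrupted temporarily for any individual subject in case of an AE as per the Investigator's discretion". Section 6.4 records incomplete doses. Section 7.1 says that stopping treatment does not end study participation. SAP section 7.9.1 has dose-intensity categories both below and above 100%.

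**The concern.** A concentration drawn before a dosing deviation cannot have been changed by it. Under Protocol Table 5 the Day 29 and Day 57 samples are taken before the dose of that day, so a missed, incomplete or excess dose on Day 57 first shows in the Day 85 sample. Yet the set has only two states for a subject, in or out. If the blinded review judges that the deviation could affect PK, the Day 1 2-hour, Day 15, Day 29 and Day 57 values leave the summaries along with the later ones.

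What is at stake is the description of the concentration profile, and in particular the trough summaries used to judge approach to steady state (Protocol section 9.4.9.2). These would rest on fewer subjects than have valid data, and only on subjects with uneventful dosing throughout. Protocol section 8.2.1.9 also asks the investigator, after an overdose, to "Obtain a serum sample for PK analysis soon after the dose for SC administration". The same subject could then be left out of the set used for PK analyses.

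**Working it through.** The plan gives no figure for this point, so there is none to reproduce. The loss can be counted from the sampling schedule.

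**Inputs**
- Post-dose samples per subject (Protocol Table 5; SAP Table 7): Day 1 at 2 hours, Day 15, Day 29 predose, Day 57 predose, Day 85, Day 141 = 6.
- Doses on Days 1, 29 and 57.
- About 120 subjects randomized 1:1:1 (Protocol section 9.2), so 40 per arm and 2 × 40 = 80 on imsidolimab. Scheduled post-dose samples: 80 × 6 = 480.
- Share of subjects excluded for a PK-affecting dosing event: not in the documents. Assumed range 5%, 10%, 20%.

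**Samples that precede the event**
- Event at the Day 29 dose: Day 1 2-hour, Day 15, Day 29 predose = 3 of 6. Of the three trough days, 1 (Day 29) is unaffected.
- Event at the Day 57 dose: those three plus Day 57 predose = 4 of 6. Of the three trough days, 2 (Days 29 and 57) are unaffected.
- Event at the Day 1 dose: none, so subject-level exclusion costs nothing extra there.

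**Unaffected concentrations lost** = excluded subjects × 3 (all events on Day 29) to × 4 (all on Day 57).

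**Standard error of an arm mean** is SD/√n. With the SD unchanged and complete sampling, the ratio after exclusion is √(40/n remaining). It applies at visits where all the excluded values were valid: Day 1 2-hour, Day 15 and Day 29.

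| Assumed share | Excluded of 80 | Unaffected values lost | Share of 480 | n per arm | SE ratio |
|---|---|---|---|---|---|
| 5% | 4 | 4×3 to 4×4 = 12-16 | 2.5%-3.3% | 38 | √(40/38) = 1.026 |
| 10% | 8 | 8×3 to 8×4 = 24-32 | 5.0%-6.7% | 36 | √(40/36) = 1.054 |
| 20% | 16 | 16×3 to 16×4 = 48-64 | 10.0%-13.3% | 32 | √(40/32) = 1.118 |

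With sample-level exclusion, the same subjects would keep 3 or 4 of their 6 post-dose values in the summaries instead of none.

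**The case against.** Much of the case on the other side stands.

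- Exclusion is not automatic. Neither document says that a missed Day 57 dose or an interruption must remove a subject; the blinded review has to judge that PK could be affected. So the rule can remove valid values, and how often it would do so is unknown.
- Nothing is destroyed. Protocol section 9.4.1 puts all data in by-subject listings, and SAP section 7.2 lists the reasons for exclusion from the PK set.
- The overdose sample is not a contradiction. Drawing and listing it is compatible with leaving it out of nominal-dose summaries.
- The 10% in Protocol section 9.2 is assumed discontinuation before Week 12. It is not a rate of PK-affecting events, and discontinuation is not said to trigger exclusion.
- The PK objective is exploratory, the planned output is descriptive, and SAP section 6.3 drops noncompartmental analysis. No efficacy or safety conclusion depends on it.

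A reader might also infer that subjects whose dosing was changed by an adverse event would be lost from any exposure-safety analysis, and that this biases it towards no relation. The documents do not support that. Protocol section 8.3.2 says only: "Samples collected for analyses of imsidolimab serum concentration also may be used to correlate exposure to safety or efficacy". It names no analysis set. Population PK and PK/response work is optional and would have its own plan (Protocol section 9.4.9.4; SAP section 6.3). Extent of exposure, safety and anti-drug antibody data are summarized on the Safety Analysis Set (SAP section 5.5). The loss would follow only if the optional work were treated as a PK analysis. Even then the direction of bias would depend on the exposure measure and the timing of the event, and neither is specified.

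Protocol section 9.4.9.1 defers PK data handling to a separate plan that is not available here. That plan is not said to change the set definition, so the central point remains: the review has no option between keeping a subject whole and removing the subject whole.

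**Conclusion.** The point holds as a cheap improvement. As written, both documents exclude subjects and not samples, so a dosing deviation on Day 29 or Day 57 can take 3 or 4 valid post-dose concentrations per subject out of the PK summaries and trough plots. Over the assumed range of 5% to 20% of imsidolimab subjects, this means 12 to 64 unaffected values out of about 480 and a standard error about 2.6% to 11.8% larger at unaffected visits. These sizes rest on assumed event rates, one event per excluded subject, full arms of 40 with complete sampling, an unchanged SD, and a blinded review that does exclude the subject. The consequence is limited to an exploratory, descriptive objective. Neither an effect on exposure-safety analyses nor a direction of bias is established.

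**What to change.** In Protocol Table 7 and SAP section 5.4, define the PK Analysis Set as all imsidolimab-treated subjects in the safety set with at least 1 quantifiable post-dose sample, and remove the subject-level exclusion for events and deviations. In SAP section 7.6, add a sample-level rule. At the blinded review already planned, flag each concentration affected by an event or deviation, normally those from the event onward. Omit only the flagged values from the nominal-day summaries and the trough tables and plots, and list them with the reason for each flag.

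The cost is a wording change in two documents, one paragraph in SAP section 7.6 and one flag in the PK dataset. The downside is that the number of subjects will differ by visit in the concentration tables, so each table should show n by visit. The change should be made before decisions on the PK set are taken.

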9.4 STATISTICAL ANALYSES

9.4.1 GENERAL APPROACH

The statistical analysis will be performed using SAS® Version 9.4 or higher. All details regarding the statistical analysis and the preparation of tables, listings, and figures will be described in the Statistical Analysis Plan (SAP).

Efficacy and Safety of Imsidolimab in Subjects with Acne Vulgaris
Protocol ANB019-209

Version 1.0
11 February 2021

The default summary statistics for continuous variables include number of contributing observations, mean, SD, median, minimum, and maximum. For PK parameters, coefficient of variation (CV) and geometric mean will also be presented, as appropriate.

For categorical variables, the number and percentage (percentage of subjects in each category relative to the total number of subjects in the relevant analysis set or relative to the total number of subjects in the relevant analysis set with assessments available [where appropriate]) in each category will be the default summary presentation.

Unless otherwise specified, “Baseline” is defined as the last observed value of the parameter of interest prior to the first intake of study treatment (this includes unscheduled visits). For numerical variables, change from Baseline will be calculated as the difference between the value of interest and the corresponding Baseline value.

Unless otherwise specified, all formal statistical tests will be 2-sided at the 10% significance level. Point estimates of treatment differences will be accompanied with 2-sided 90% confidence intervals (CIs), where applicable.

In the case of normality assumption violations, appropriate nonparametric methods may be used for analysis.

All data will be presented in by-subject listings.

9.4.2 SUBJECT DISPOSITION

A tabular presentation of the subject disposition will be provided. It will include the number of subjects screened, randomized, treated, completed as well as the number of dropouts with reasons for discontinuation, and major protocol deviations or violations.

A listing will be presented to describe dates of screening, assigned treatment, screen failed with reason, completion or early withdrawal, and the reason for early discontinuation, if applicable, for each subject. A list of protocol deviations/violations will be identified and discussed with the Investigator/AnaptysBio in dry run to categorize as major or minor with decisions of exclusion from analysis sets prior to unblinding.

During the COVID-19 pandemic, protocol deviations related to COVID-19 will be documented and information on how they will be handled in the analyses will be detailed in the SAP.

9.4.3 BASELINE DESCRIPTIVE STATISTICS

Subject characteristics obtained at Baseline will be summarized for all subjects taking imsidolimab or placebo.

Efficacy and Safety of Imsidolimab in Subjects with Acne Vulgaris
Protocol ANB019-209

Version 1.0
11 February 2021

Summaries will include descriptive statistics for continuous variables (sample size [n], mean, SD, median, minimum, and maximum) and for categorical variables (n, frequency, and percentage).

Medical history will be coded using the Medical Dictionary for Regulatory Activities (MedDRA) latest version and listed for all subjects.

9.4.4 CONCOMITANT MEDICATION

All medications will be coded using the World Health Organization (WHO) Drug Dictionary and Anatomical Therapeutic Chemical (ATC) system. Each medication will be classified as prior medication if it is stopped prior to the first dose of study treatment, or as concomitant medication if it is ongoing at the time of the first dose or is started after the first dose of study treatment. Prior, concomitant, and rescue medications will be summarized descriptively with a by-subject listing.

To handle the issue of rescue medication use, the efficacy data on and after the use rescue medication will be set to missing in the efficacy analysis.

9.4.5 ANALYSIS OF THE PRIMARY EFFICACY ENDPOINT

The primary efficacy endpoint is the change from Baseline in facial inflammatory lesion count at Week 12.

A general linear mixed model repeated measures (MMRM) analysis will be used to estimate the least-squares means (LSM) and associated standard errors for the change from Baseline in facial inflammatory lesion count to Week 12. The model will include change from Baseline in facial inflammatory lesion count at Week 12 as the dependent variable, fixed effects for treatment arm, categorical time point, and the treatment by time point interaction, and the Baseline facial inflammatory lesion count and the stratification factor (ie, facial IGA score at baseline) as covariates. An unstructured covariance structure will be used. The difference between LSMs (imsidolimab – placebo) at Week 12 will be presented along with the associated 90% CI and p-value.

Possible effect of any other covariates as well as investigation of variables through sub-group analysis may also be investigated.

9.4.6 ANALYSIS OF THE SECONDARY EFFICACY ENDPOINTS

Following are the secondary efficacy endpoints:

- Change from Baseline in facial inflammatory lesion counts at visits other than Week 12
- Percent change from Baseline in facial inflammatory lesion counts at each visit

Efficacy and Safety of Imsidolimab in Subjects with Acne Vulgaris
Protocol ANB019-209

Version 1.0
11 February 2021

- Change from Baseline in facial noninflammatory lesion counts at each visit
- Percent change from Baseline in facial noninflammatory lesion counts at each visit
- Change from Baseline in total facial lesion (inflammatory and noninflammatory lesions) counts at each visit
- Percent change from Baseline in total facial lesion (inflammatory and noninflammatory lesions) counts at each visit
- Change from Baseline in Facial IGA at each visit
- Proportion of subjects achieving a Facial IGA of clear (0) or almost clear (1) with at least a 2-grade decrease from Baseline at each visit
- Proportion of subjects in each response category for the PGIS at each visit
- Proportion of subjects in each response category for the PGIC at each post-Baseline visit
- Change from Baseline in DLQI/CDLQI at each visit

